7.6 Data Management

All reports and deliverables will contain aggregated results only and will not identify individual patients, physicians, or facilities. Optum Epidemiology and other potential research partners will conduct the analyses at their own sites, with Optum Epidemiology conducting the meta-analyses, and Galderma will not have access to individual level data.

For the ORD and Optum’s Market Clarity data, high-level access to data platforms and data assets are controlled through an internal application that requires individuals to request individual access to specific environments and data. The ORD is maintained on a Teradata server with access to the database and individual project-specific folders controlled with an internal application, while Optum’s Market Clarity data is stored in a secure Amazon Web Service S3 bucket within Optum’s de-identified data warehouse. Project-specific data is extracted and downloaded to our Statistical Analysis System (SAS) Unix server where it is stored within project-specific folders with access limited to those on or supporting the project team. Users are required to complete ORD Privacy and Compliance training commensurate with their requested access role prior to gaining access, policy, or other appropriate means. Users are required to comply with any limits, qualifications, conditions, or restrictions set forth in the de-identification determination.

The data management team ensures that identification numbers are not derived from or related to other system or external IDs (such as social security number) or other information about the individual data subjects whose de-identified data is contained in the ORD, as set forth in 45 C.F.R. Section 164.514(b)(2)(i)(R). The Lockbox contains direct identifiers that may be used to re-identify an individual, but can only be accessed and used for re-identification after appropriate approvals are obtained.

7.7 Data Analysis

All analyses will be conducted using SAS version 9.4 (SAS Institute Inc., Cary, North Carolina) and SAS Enterprise Guide 6.1 or later.

7.7.1 Annual Monitoring

Optum will tabulate counts of pregnancies exposed to nemolizumab (from 95 days [i.e., 5 times the half-life], or approximately 14 weeks, before ECD through the end of pregnancy) as well as counts of live births from these pregnancies, and the results will be included in the PSURs. Women with nemolizumab-exposed pregnancy episodes will be described according to baseline demographic and clinical characteristics (a subset of those mentioned in [Section 7.4.3](#)). Additionally, the overall number of eligible pregnancies will be tabulated and described according to the same baseline demographic and clinical characteristics. All analyses will be descriptive, including the number of observations, mean, standard deviation, median, interquartile range, and range for all continuous variables and counts and percentages for each binary or categorical variable. Counts from Optum's Market Clarity Data will be added starting with the 2029 PSUR, and additional data partners will be added based on the results of the feasibility assessment to ensure sample size projections are met (as described in [Section 7.7.2](#)).

Outcome counts (except for live births), matching, propensity score estimation, meta-analyses, and sensitivity analyses will not be performed until the final report.

7.7.2 Feasibility Assessment

As additional data sources will be needed to meet sample size projections for the study of rare pregnancy and infant outcomes, a feasibility assessment will be submitted as part of the 2029 PSUR. This assessment will consist of a count request and a questionnaire completed by potential data sources. All potential data sources will be asked to provide counts of nemolizumab-exposed pregnancies by year using the same methods employed by Optum for the counts included in the PSURs. Potential data sources will also be asked to complete a questionnaire that evaluates data quality and operational aspects needed to conduct the study. This survey will include questions regarding the ability to identify pregnancies and exposure to treatments, conduct mother-infant linkage, and identify outcomes of interest. There will also be questions regarding population size, geographic distribution, length of follow-up, data completeness, processes and timeline for data access and ethics approval, data lag time, and frequency of data updates. The feasibility assessment questionnaire will be included in the SAP.

7.7.3 Final Analysis

For the final study report, Optum will match nemolizumab-exposed pregnancies to the two comparator groups (Other AD/PN Treatment Cohort and Unexposed Cohort) in a 1:4 ratio based on maternal age at cohort entry, gestational week of dispensing, indication, and calendar week, separately within each data source. If the study size does not permit matching in these categories (or intervals), the sequential cohorts may be collapsed to 2-week intervals for gestational week at cohort entry or wider categories for maternal age at cohort entry and calendar time. A variable matching ratio of 1:up to 4 may also be considered.

7.7.3.1 Propensity Score and IPTW

In the final study report, comparative analyses will be performed incorporating stabilized IPTW to adjust for potential confounding. The stabilized IPTW will be appropriately defined such that the causal estimate is the average treatment effect in the treated (ATT; [Austin and Stuart, 2015](#)). Briefly, to estimate the ATT, the weights are defined such that every nemolizumab-exposed pregnancy receives a weight of 1, while the comparator pregnancies receive weights that are a function of the propensity score. Each pregnancy's propensity score (the probability of receiving nemolizumab versus a comparator or no treatment, given membership in the study population and a set of covariates) will be estimated using a logistic regression model with exposure status as the outcome (dependent variable). A total of 2 propensity score models will be generated: one for the comparison of the Nemolizumab Cohort versus Other AD/PN Treatment Cohort and another for the comparison of the Nemolizumab Cohort versus the Unexposed Cohort. The covariates listed in [Section 7.4.3](#) (excluding Sections 7.4.3.6 and 7.4.3.7) will be considered for inclusion in the model as independent (predictor) variables. The propensity score model will only include covariate information from cohort entry or earlier. In addition to the pre-specified variables in [Section 7.4.3](#), the most common diagnoses, procedures, and medications observed prior to ECD will be evaluated to ensure no important confounders are missed.

If there are too many variables given the number of pregnancies exposed to nemolizumab (e.g., < 10 exposed pregnancies for every variable in the propensity score model), the number of variables may be reduced. For variable pairs that are highly correlated (e.g., correlation coefficient > 0.9), one may be eliminated.

Balance between the cohorts will be evaluated before and after weighting. Variables with an absolute standardized difference < 0.1 will be considered balanced. If a variable has an absolute standardized difference ≥ 0.1 , the imbalanced covariate will be included in the outcome model. Overall balance between the cohorts, both before and after weighting, will be assessed via overlap (or lack thereof) in histograms of the propensity score. The distribution of weights will also be inspected. To address the impact of large weights on the analysis, truncation of weights greater than 10 will be considered.

7.7.3.2 Descriptive Analysis

The final study report will include a flow chart that describes the number of pregnancies among women with moderate to severe AD or PN that meet all study eligibility criteria. The number of pregnancies included in each exposure window and in each study cohort, live births, linked infants and pregnancy and infant outcomes will be described.

Similar tables of study covariates will also be provided among the subset with pregnancy or infant outcomes of interest to identify likely risk factors for outcomes and compare mothers of linked infants to mothers of non-linked infants to evaluate the potential for selection bias in the analysis of infant outcomes that are by necessity restricted to pregnancies with linked infants.

The study population will be described by study cohort according to the characteristics listed in [Section 7.4.3](#), before and after IPTW. Prevalence and a corresponding 95% confidence interval will be estimated for MCMs and SGA births. Prevalence will be estimated for these outcomes

because they develop during gestation but are only observable at birth; thus, only the prevalence at birth can be calculated. Incidence and a 95% confidence interval will be estimated for all other study outcomes, which are observable as they arise. For each outcome, the prevalence or incidence will be calculated before and after weighting. Analyses will be conducted on MCMs collectively as a whole, and among specific malformations or subgroups of malformations, as sample size allows. The number of pregnancies with each outcome will guide the analyses that are feasible.

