7.3.2 Inclusion Criteria

Pregnancies among women who meet the following criteria will be eligible for inclusion in the study:

- An ECD between 12 August 2024 and 31 March 2032
- For claims data sources, continuous health plan enrollment with complete medical and pharmacy benefit coverage from 6 months before and including cohort entry (only applicable to the pregnant woman)
- For linked claims-EHR data sources:
 - Pharmacy (but not medical) coverage during the full pregnancy period (as described in [Table 1](#)) will be required to ensure dispensings of cohort defining drugs are captured. (A shorter period of continuous enrollment will be required for linked claims-EHR data sources compared with the claims databases because pharmacy claims will be used primarily for exposure assessment, while covariates will be assessed from the EHR data).
 - Presence of at least one outpatient clinical visit at least 6 months prior cohort entry (to establish a 6-month baseline period for assessment of AD and PN as well as clinical covariates).
- Evidence of moderate to severe AD or PN ascertained using appropriate algorithms

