Stillbirth	Entire pregnancy	Week 2 – Week 40	Later of cohort entry or 20 weeks + 0 days	End of pregnancy, disenrollment from the health plan/8 weeks of no clinical activity, or the end of the study period
MCM	First trimester	Week 2 – Week 13	Delivery	First year of life, disenrollment from the health plan/8 weeks of no clinical activity, or the end of the study period
SGA birth	Entire pregnancy	Week 2 – Week 40	Delivery	First year of life, disenrollment from the health plan/8 weeks of no clinical activity, or the end of the study period

Abbreviations: ECD, estimated conception date; EHR, electronic health record; MCM, major congenital malformation; SGA, small for gestational age

¹ For individuals with a cohort entry date after the pre-specified start of follow-up, follow-up begins at cohort entry. For example, for cohorts beginning at 24 gestational weeks, follow-up for stillbirth will begin at 24 gestational weeks.

² For EHR and linked claims-EHR data sources, pregnancies will be censored at the end of 8 weeks of no clinical activity. Since pregnant women should regularly interact with the healthcare system, this censoring criterion will indicate loss to follow-up in the database.

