7.4.2.2 Infant Outcomes

7.4.2.2.1 MCM

MCMs will be defined based on guidelines from the New York State Department of Health Congenital Malformations Registry, National Birth Defects Prevention Network, and/or the European Surveillance of Congenital Malformations. Live births will be followed for up to one year to identify MCMs that may not be detected until after birth. All identified MCMs will be counted, overall, and classified by body system. Operational definitions may be modified to add or remove MCM-specific ICD-10-CM codes based on clinician input or newly identified algorithms in the literature. Minor congenital malformations will not be included in this definition. A list of ICD-10-CM diagnosis codes for MCMs can be found in [Appendix E](#).

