7.4.3.7 Infant Covariates

Infant covariates will be assessed during the first year of life and included in descriptive analyses only (not in propensity score models):

- Sex
- Multiple birth vs singleton birth
- Duration of continuous medical and pharmacy coverage (in claims databases only)

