7.5 Study Size

Table 3 presents the minimum number of nemolizumab exposed pregnancies required to detect relative risks equal to or greater than 2.0, 2.5, or 3.0 for a comparative analysis of each of the study outcomes, assuming a ratio of 1:4 exposed to unexposed, 80% power, a 2-sided alpha of 0.05, and the referenced outcome prevalences. For infant outcomes, the minimum number of nemolizumab-exposed livebirths was calculated, and the number of nemolizumab-exposed pregnancies was derived from these counts based on the prevalence of live birth. For the primary outcome MCM, a study size of 214 live births with linked infants exposed to nemolizumab in the first trimester exposure window would provide an 80% power to detect a RR of 2.5, and 133 live births with linked infants exposed to nemolizumab in the first trimester exposure window would provide 80% power to detect a RR of 3. Assuming 80% of pregnancies have an observed outcome and 76% of observed outcomes are live births, an estimated 352 pregnancies exposed to nemolizumab during the first trimester would need to be accrued to detect a RR of 2.5 and 219 exposed pregnancies to detect a RR of 3. With a 1:4 ratio of exposed to unexposed, this corresponds to 1,408 pregnancies (for 2.5) or 876 (for 3) in each comparator group.

Table 3 Sample size required for 80% power to detect effect estimates for pregnancy and infant outcomes, with 1:4 matching¹

Outcome	Prevalence of Outcome	Relative Risk	Nemolizumab Exposed Pregnancies Needed	Nemolizumab Exposed Live Births Needed
MCM	3% ²	2	709	431
		2.5	352	214
		3	219	133
Ectopic pregnancy	1-2%	2	877	N/A
		2.5	438	
		3	275	
Elective termination	21%	2	45	N/A
		2.5	21	
		3	12	
Preterm birth, SGA birth	10% ^{3,4}	2	190	115
		2.5	94	57
		3	56	34
Spontaneous abortion	14% ⁵	2	77	N/A
		2.5	37	
		3	22	
Stillbirth	1% ⁶	2	1,324	N/A
		2.5	662	
		3	415	

Abbreviations: N/A, not applicable; SGA, small for gestational age

¹ Calculations were performed via www.OpenEpi.com using the Fleiss method, as described in Fleiss JL. Statistical Methods for Rates and Proportions. John Wiley & Sons, 1981.

² March of Dimes. Perinatal Data Snapshot: United States Birth Defects. 2015; http://www.marchofdimes.org/peristats/pdflib/999/pds_99_4.pdf.

³ Centers for Disease Control and Prevention. Quick Stats: Percentage of Small for gestational-Age Births, by Race and Hispanic Ethnicity—United States, 2005. MMWR. 2008;57(50):1359. <https://www.cdc.gov/mmwr/preview/mmwrhtml/mm5750a5.htm>.

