7.7.3.3 Comparative Analyses

Nemolizumab-exposed pregnancies will be matched to pregnancies in the two comparator groups in a 1:4 ratio based on maternal age at cohort entry, gestational week of dispensing, indication, and calendar week, separately within each data source. For all pregnancy and infant outcomes assessed at the end of pregnancy or during pregnancy, we will estimate RRs comparing the Nemolizumab Cohort to the comparator cohorts using robust Poisson regression models (for MCMs and SGA births) and HRs using Cox proportional hazards models (for all other outcomes). All comparative analyses will be performed incorporating stabilized IPTW to adjust for potential confounding. All analyses will be conducted by data source and then meta-analyzed (as described in [Section 7.7.3.4](#)).

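### The primary MCM measure is fixed as prevalence at birth, yet MCMs are ascertained over a first year that can be cut short, and the protocol states no handling for infants who leave early

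*Protocol*

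**What the plan says.** Four parts of the protocol bear on how MCM is measured.

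- **Measure.** Section 7.7.3.2 chooses prevalence for MCMs and SGA births "because they develop during gestation but are only observable at birth; thus, only the prevalence at birth can be calculated". All other outcomes get incidence.
- **Ascertainment.** Section 7.4.2.2.1 states: "Live births will be followed for up to one year to identify MCMs that may not be detected until after birth". Table 2 (7.3.6.2) starts MCM follow-up at delivery and gives as censoring events "First year of life, disenrollment from the health plan/8 weeks of no clinical activity, or the end of the study period". Section 7.3.6.7 repeats these end points for each linked infant.
- **Model.** Section 7.7.3.3 estimates RRs "using robust Poisson regression models (for MCMs and SGA births) and HRs using Cox proportional hazards models (for all other outcomes"). No offset, censoring weight or fixed infant window is given.
- **Infant follow-up.** The claims-data enrolment criterion in 7.3.2 is "only applicable to the pregnant woman", and no minimum is set for the infant. Infant coverage duration appears in 7.4.3.7, where: "Infant covariates will be assessed during the first year of life and included in descriptive analyses only".

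The study size in 7.5 is computed "assuming a ratio of 1:4 exposed to unexposed, 80% power, a 2-sided alpha of 0.05, and the referenced outcome prevalences". For MCM the prevalence is 3%, and 214 exposed linked live births "would provide an 80% power to detect a RR of 2.5".

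**The concern.** The sections on measure and ascertainment cannot both be right for MCM. If malformations were observable only at birth, a one-year search and a list of infant censoring events would have no purpose. If some are first coded months later, the proportion of linked infants with a code depends on how long each infant stayed in the data.

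A yes/no outcome with no minimum follow-up and no censoring adjustment gives an infant enrolled for a few weeks the same non-case status as one followed for the full year. Three things are at stake:

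- **Frequency.** The MCM frequency is a stated objective. It would be neither prevalence at birth nor one-year risk, and it would fall as infant turnover rises.
- **Power.** The calculation assumes that 3% of comparator infants are detected cases, with no allowance for late diagnoses that are missed.
- **Relative risk.** If infants of exposed women leave earlier or later than comparator infants, and late coding is common enough to matter, the RR is shifted. Results from sources with different turnover are then meta-analysed.

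**Working it through.** **Step 1: reproduce the plan's figure.** Inputs from 7.5: comparator risk p0 = 0.03, RR 2.5 so p1 = 0.075, ratio r = 4, two-sided alpha 0.05, power 80%, Fleiss method. Without continuity correction:

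n1 = [1.960·√((r+1)·p̄·(1−p̄)) + 0.8416·√(r·p1(1−p1) + p0(1−p0))]² / [r·(p1−p0)²], where p̄ = (p1 + r·p0)/(r+1) = 0.039.

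- First term: 1.960 × √0.1874 = 0.848.
- Second term: 0.8416 × √0.3066 = 0.466.
- n1 = 1.314² / 0.0081, which rounds up to 214.
- Pregnancies: 214/(0.80 × 0.76) = 352.

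Both match the protocol. Power at 214 against 856 is 80.1%. Neither step has a term for infants lost during the first year.

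**Step 2: share of cases missed.** The protocol gives no infant turnover and no age at first MCM code, so both are assumed. Let d be the share of linked infants who leave before one year, uniformly over the year. Let q be the share of MCMs first coded after the birth stay, also uniformly over the year. For a leaver with a late-coded MCM, the chance that coding falls after leaving is 1/2. The share of cases missed is therefore d·q/2.

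**Step 3: equal loss in both cohorts, true RR 2.5.**

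| d | q | Missed | Observed comparator risk | Power at 214 v 856 | Live births / pregnancies for 80% |
|---|---|---|---|---|---|
| 0 | – | 0% | 3.00% | 80.1% | 214 / 352 |
| 20% | 30% | 3% | 2.91% | 79.0% | 221 / 364 |
| 40% | 60% | 12% | 2.64% | 75.5% | 244 / 402 |

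Both risks are scaled by the same factor, so the RR stays at 2.5. A harsher assumption is that 40% leave and half of their MCMs are still uncoded when they go. That misses 20% of cases and gives 2.40% observed risk and 72.0% power.

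**Step 4: unequal loss.** The RR is multiplied by (1 − d1·q/2)/(1 − d0·q/2). With q = 50%:

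- 40% of exposed and 20% of comparator infants leave: 0.90/0.95 = 0.947, so a true RR of 2.5 reads as 2.37.
- The reverse, 20% and 40%: 0.95/0.90 = 1.056, so 2.5 reads as 2.64.

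If q is near zero the multiplier is near 1 whatever the turnover.

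**Step 5: look for a stated safeguard.**

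- Section 7.10 compares baseline characteristics only for pregnancies censored before the end of pregnancy. It also promises censoring frequencies by exposure status, which could include infants.
- Section 7.7.3.2 compares mothers of linked and non-linked infants, not short and full infant follow-up.
- The MCM bias analysis in 7.7.3.5.8 concerns pregnancies without a live birth.
- The misclassification analysis in 7.7.3.5.7 is general and does not name truncated infant follow-up.

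These give some view of the problem. None defines how a censored infant enters the MCM estimate.

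**The case against.** An MCM is present at birth, and the year is a window for detecting it, not time at risk. On that view prevalence at birth is a defensible target, and the sentence in 7.7.3.2 is only loosely worded. Much of this stands. But a target of prevalence at birth still needs a rule for infants not observed long enough for detection, and the stated reason remains wrong for MCM.

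A reader might infer more than the protocol supports, in four ways:

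- **That the protocol says early leavers are malformation-free.** It does not. The absence-of-code rule in 7.7.4 is drawn out there for covariates. Counting early leavers as non-cases follows from a binary outcome with no minimum follow-up.
- **That robust Poisson cannot deal with censoring.** It can carry censoring weights or an offset, and the statistical analysis plan, not available here, may add one. An offset would, however, give a rate ratio in place of the stated prevalence and RR.
- **That infant coverage dates may not be used.** The limit in 7.4.3.7 goes with keeping those variables out of the propensity score. Follow-up under 7.3.6.7 needs the dates in any case.
- **That differential loss would go unseen.** Description of infant coverage by cohort, censoring frequencies by exposure and the misclassification analysis would partly reveal it, and 7.7.3.4 includes heterogeneity diagnostics.

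The magnitudes are also modest and wholly assumed. The protocol gives no reason to expect twofold differential turnover, and 6 states no a priori hypotheses, so a few points of power change no decision rule.

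**Conclusion.** The point holds in a limited form. The rationale in 7.7.3.2 contradicts 7.4.2.2.1, Table 2 and 7.3.6.7 for the primary outcome, and no stated step handles infants censored before one year. Run as written, the MCM frequency would mix infants with different lengths of observation and would depend on each source's turnover.

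The claim that the RR is biased whenever coverage differs is too strong. Bias needs both unequal infant follow-up between cohorts and an appreciable share of late-coded MCMs. Equal loss, with few false positive codes, leaves the RR essentially unbiased and costs only frequency and power.

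Under the assumed 3% to 12% of cases missed, power falls from 80.1% to between 79.0% and 75.5%. Under 40% against 20% loss with half of MCMs coded late, the RR is multiplied by about 0.95. If most MCMs are coded near birth, the effect is small. This merits a change because it concerns the primary safety estimate and can be settled before extraction starts in December 2032 (section 4), not because a large error is shown.

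**What to change.** - Correct the rationale in 7.7.3.2 for MCM. SGA can stay as planned.
- Keep robust Poisson in 7.7.3.3, but define the MCM measure as risk from birth to one year with infant censoring handled. Examples are inverse-probability-of-censoring weights combined with the ATT weights, or weighted one-year cumulative risks and their ratio.
- Report MCMs coded at or near birth as a separate measure, with the window stated.
- Add a sensitivity analysis in infants with complete first-year follow-up.
- Report infant censoring, by reason, for each cohort and data source.
- In linked claims-EHR sources, check the 8-week inactivity rule before using it to censor infants. Its footnote in Table 2 is argued for pregnant women. If healthy infants are seen less often, they would be censored sooner, and one-year risk would be overstated.

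The cost is wording in two sections, some programming and slightly wider intervals. The follow-up end dates are already needed under 7.3.6.7. Section 7.4.3.7 lists coverage duration for claims databases only, so other sources need their own end-of-observation date.
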